Lipid intake in the neonatal period is crucial for retinal and brain development along and an important source of calories for growth [16]. Due to this essential nature of lipid intake during the neonatal period, concern has been raised regarding lipid restriction and its effects on neonatal growth and neurodevelopmental outcomes. Studies investigating neurodevelopmental outcomes of infants treated with lipid restriction have shown development within normal ranges for the patient's age and similar to those of patients treated with standard soy-based lipid dosing [17, 18]. Studies have shown mixed results with regards to growth and neonates treated with lipid restriction. Rollins et al showed a greater increase in weight z-score for patients on standard soy-based dosing compared to reduced dosing, but found no difference in length or head circumference [13]. Other studies have found similar growth when comparing patients both in the neonatal period and into early childhood [18, 19]. The role of the various lipid strategies in the prevention of IFALD is still unclear at this time. Further studies are needed to better understand this disease, its prevention, and its outcomes. During this study we hope to compare two possible preventative strategies and determine a future direction for studying Smoflipid and soy-based lipid reduction.

Specific Aim

This study is designed to be a single center, pilot study to evaluate the prevention of cholestasis in neonates requiring abdominal surgery with intestinal failure, divided into two treatment groups, one receiving composite lipid emulsion (Smoflipid® 20%) at standard dosing and the other receiving soy-based lipid (Intralipid® 20%) at reduced dosing. The rate of cholestasis development in the two treatment groups will be compared to a historical control cohort which received soy-based lipid (Intralipid® 20%) at standard dosing of 2 to 3 g/kg/d .

Study Objectives

1. Primary: The primary objective of this study is to determine the number of infants receiving Smoflipid at typical dosing (2-3 g/kg/d) and the number of infants receiving Intralipid reduction (1 g/kg/day) that develop cholestasis compared to historical controls receiving Intralipid at standard dosing (2-3 g/kg/day). Cholestasis will be defined as direct bilirubin greater than 2 mg/dL for at least two measurements, 5-7 days apart.

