2. Secondary (comparison of each listed parameter between the prospective treatment groups in addition to comparison of each treatment group with historic controls):
 - a. Growth (rate of change)

- i. Weight, length, and head circumference at enrollment, on a weekly basis while receiving study lipid, and 2-3 weeks post-study lipid completion.
- ii. Weight, length, and head circumference at 36 weeks corrected gestational age and time of discharge.
- b. Essential fatty acid profile differences and development of deficiency
- c. Average total caloric intake for all patients on weekly basis
 - i. Average lipid dose delivered on weekly basis
- d. Feeding tolerance/ percentage of total calories from enteral feeds
 - i. Time to achievement of enteral autonomy (full enteral feedings)
 - ii. Percentage of enteral calories at end of study
 - iii. Percentage of patients in each group with enteral autonomy
- e. Transaminase, alkaline phosphatase, GGT levels at enrollment, every 4 week time point, and end of study
- f. Triglyceride concentration at baseline, weekly, and end of study
- g. Rates of other diagnoses in each study group
 - i. Retinopathy of prematurity as diagnosed by Ophthalmologic examination
 - ii. Chronic lung disease as defined by need for oxygen at time of discharge or 36 weeks corrected gestational age (if at least 28 days of age), whichever comes first.
- h. Rates of adverse and serious adverse events in each group
- i. Length of stay
- j. Two year neurodevelopmental differences using ASQ-3 screening

Study Population

Inclusion criteria

Infants admitted to the Riley Hospital Neonatal Intensive Care Unit (NICU), regardless of postmenstrual or corrected gestational age, with anticipated need for parenteral nutrition for four or more weeks PLUS one or more of the additional inclusion criteria listed below will be eligible for inclusion within the study and for randomization. Inclusion criteria include:

- Anatomic intestinal defect: Neonate with intestinal atresia, omphalocele, gastroschisis or volvulus with or without intestinal resection and need for parenteral nutrition pre or post-operatively.
- Ischemic/perforation intestinal injury: Neonates with spontaneous intestinal perforation or necrotizing enterocolitis requiring surgical intervention with need for parenteral nutrition post-operatively.

Exclusion criteria at time of study enrollment

- Infant with current weight less than 750 grams

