- AST or ALT greater than 5 times the upper limit of normal within 2 weeks of enrollment

- Direct bilirubin greater than 2 mg/dL on any consecutive measurement 5-7 days apart within 2 weeks of enrollment
- Severe coagulopathy with elevated INR greater than 2.0 or clinically significant bleeding as determined by the primary and research teams
- Culture confirmed sepsis with positive blood, urine, or CSF culture within 2 weeks (14 days) of enrollment
- Renal failure requiring dialysis
- Cyanotic heart disease requiring prostaglandin therapy
- Hypertriglyceridemia (greater than 250mg/dL) at time of enrollment

Enrollment/Randomization

A maximum total of 50 prospective patients, 25 per arm, will be enrolled in the study. Patients will be eligible for enrollment if they meet the above listed enrollment criteria. Once patients are determined to meet enrollment criteria, the parents of the patient will be approached and informed consent will be obtained. Please see separate informed consent document for full consent details.

Stratified randomization will be used to divide patients into each treatment group. Patients will be initially stratified based on the diagnosis of necrotizing enterocolitis or spontaneous intestinal perforation (ischemic/perforation group) or anatomic intestinal abnormality. Once stratified based on diagnosis, patients in each stratum will then be randomized to receive either Smoflipid or Intralipid reduction as described below. Group randomization will be based on premade concealed envelopes.

This study will not be blinded as the caloric dose of the lipid strategies will vary and potentially influence other TPN dosing. Both IV lipids will be given as a solution separate from the remaining TPN. This separate IV lipid will be given as two 12 hour infusions over a 24 hour period.

In the event of slower than anticipated patient enrollment, a minimum of 24 patients (12 per treatment group) will be enrolled in order to obtain needed feasibility data.

Historic Controls

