A group of 24 patients previously treated in the Riley NICU from the years 2016 – 2017 will be used as a historic control cohort. Historic patients will be eligible for enrollment in the study if they have one of the above listed diagnoses, received post-operative parenteral nutrition, and were treated with soy-based lipid at standard dosing (2-3 g/kg/day). Historic patients will be ineligible to participate if any of the above listed exclusion criteria are true at the time of their abdominal surgery. Historic patients will be matched to prospective patients when able. This matching will first utilize in order: 1. days of parenteral lipid therapy, 2. diagnosis, 3. birth gestational age, and 4. birth weight when selecting for inclusion.

Study Procedures

1. Smoflipid® (20% lipid emulsion) treatment group
 - a. Advancement:
 - i. Smoflipid will be started at 1 g/kg/d on day 1 of parenteral nutrition after enrollment and advanced by 1 g/kg/d each subsequent day to a goal maximum of 3 g/kg/d
 - b. Maintenance and weaning [8]:
 - i. The Table below will be used as a guide for weaning Smoflipid as enteral nutrition is initiated and advanced.
 - ii. Patients will continue to be monitored by a clinical dietitian and pharmacist as per standard of care. Pending their recommendations, along with the clinical state of the child, the actual dose of Smoflipid needed may vary by individual patient.
 - c. Other parenteral nutrition components
 - i. Amino acid will be provided to meet estimated protein requirements only and will not be increased as a form of caloric intake.
 1. Term infant approximate goal of 3 g/kg/day and preterm infant approximate goal of 3.5 – 4 g/kg/day.
 - ii. Glucose infusion will be utilized and advanced per standard protocol to provide remainder of estimated non-protein caloric need of each individual patient.
 1. Maximum glucose infusion rate (GIR) while enrolled in study of 16 mg/kg/min. If further caloric intake is required, Smoflipid will be increased to a maximum of 3 g/kg/d.

Table 1: Smoflipid dosage recommendations for weaning as enteral feeds advanced

% calories from PN	Volume enteral feeds (ml/kg/d)	Enteral calories (kcal/kg/d)	Lipid (g/kg/d)
80-100%	\leq 20-40	\leq 30	3
60-80%	40-60	30-40	3
50-60%	60-80	40-50	2.5
40-50%	80-100	50-60	2
30-40%	100-110	60-70	1.5
20-30%	120	70-90	1
<20%	>120	>90	0

2. Intralipid® (20% lipid emulsion) reduction treatment group
 - a. Advancement:
 - i. Intralipid:

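### Historic controls are selected first on lipid days that accrue after treatment starts, and need not meet the four-week PN criterion that defines the prospective cohort

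*Combined protocol and SAP*

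**What the plan says.** The Specific Aim makes the control comparison the main one: "The rate of cholestasis development in the two treatment groups will be compared to a historical control cohort". The primary objective repeats this for each arm.

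The two sides of that comparison enter by different routes.

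- **Prospective infants** (Inclusion criteria) must have a listed diagnosis and be infants "with anticipated need for parenteral nutrition for four or more weeks".
- **Historic controls** (Historic Controls, after Enrollment/Randomization) are eligible if they "have one of the above listed diagnoses, received post-operative parenteral nutrition, and were treated with soy-based lipid at standard dosing" (2-3 g/kg/day). They are ineligible "if any of the above listed exclusion criteria are true at the time of their abdominal surgery". No anticipated or actual PN duration is required.

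Selection of the 24 controls is then described in two sentences. "Historic patients will be matched to prospective patients when able", and the order is "This matching will first utilize in order: 1. days of parenteral lipid therapy, 2. diagnosis, 3. birth gestational age, and 4. birth weight". No ratio, caliper or algorithm is given. Diagnosis comes second, although it is the randomisation stratum (Enrollment/Randomization: "Patients will be initially stratified based on the diagnosis of necrotizing enterocolitis or spontaneous intestinal perforation").

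Statistical Considerations plans Fisher's exact tests for categorical outcomes and names no adjustment for the control comparisons.

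**The concern.** Matching is meant to make groups alike at the start. Realised lipid days are not a starting characteristic, and under the protocol they can depend on regimen and outcome:

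- The Smoflipid weaning guide (Table 1) reaches zero lipid while up to 20% of calories still come from PN. Reduced Intralipid is in general maintained for as long as the enrolled infant receives PN (Study Procedures 2).
- The first response to high triglycerides lowers the daily Smoflipid dose, but can move Intralipid to three days a week (Laboratory monitoring, vii). That changes the count of lipid days in one arm only.
- Direct bilirubin of 3 mg/dL or more on two draws ends study lipid. Later lipid is left to the treating physician (Stopping study Lipid).

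If a regimen works partly by shortening lipid exposure, forcing controls to have the same exposure removes that part of the effect. It also pairs treated infants with controls who had a milder course. Since selection is the only stated safeguard for comparability, the primary objective depends on it.

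**Working it through.** **Figures in the plan.** The 24 controls and 25 per arm have no power calculation or event rate behind them, so there is no stated figure to reproduce. Up to 2 x 25 = 50 infants share 24 controls, so at least 50 - 24 = 26 (52%) have no control of their own. Matching must be pooled or partial.

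**Effect of the missing criterion alone.** Let a share s of controls be short-PN infants. Control rate = s x p_short + (1 - s) x p_long. Assume s = 25-50% and p_short = 5-15%.
- p_long = 40%: from 0.25 x 15 + 0.75 x 40 = 33.75% down to 0.50 x 5 + 0.50 x 40 = 22.5%.
- p_long = 60%: from 0.25 x 15 + 0.75 x 60 = 48.75% down to 0.50 x 5 + 0.50 x 60 = 32.5%.

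Without the criterion and without any match, the control rate would be too low. Lipid-day matching counters this.

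**Worked simulation (all inputs assumed).** Lipid need is lognormal with median 35 days. Log-need is 0.5u plus noise of SD 0.3, where u is standard normal severity. The clinician's forecast is 0.5u plus noise of SD 0.2 on the same scale. Prospective infants enter if the forecast is at least 28 days. Cholestasis hazard is 0.008 x exp(0.4u) per day on lipid, capped at 84 days. There are 25 infants and 24 controls from a pool of 100, with nearest match on total lipid days where matching is used, and 1,000 repetitions.

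| Scenario | Arm | Controls | Difference (points) |
|---|---|---|---|
| No effect; no criterion, no match | 37.8% | 29.5% | +8.4 |
| No effect; lipid-day match, no criterion (as written) | 38.1% | 37.2% | +0.9 |
| No effect; criterion on controls, no lipid-day match | 37.9% | 37.8% | +0.2 |
| Lipid days 20% shorter; as written | 33.6% | 29.4% | +4.1 |
| Lipid days 20% shorter; criterion, no lipid-day match | 33.1% | 38.1% | -4.9 |

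(Differences were taken before rounding.) The true effect in the last two rows is about 33.1 - 37.9 = -4.8 points. The rule as written shows +4.1, a bias of about +8.9. The reason is simple: a treated infant who would have needed 35 days now has 0.8 x 35 = 28, and is paired with a control who needed only 28.

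**Wider ranges (all inputs assumed).** A broader simulation used source medians of 25, 32 or 40 days, hazards of 0.006 to 0.016 per day, pools of 60 or 150, and controls matched to both arms pooled. The baseline alternative applies the criterion and matches on baseline variables. Its chart-review error is given as a log-SD; the prospective forecast was given 0.42. The rows with changed duration or hazard use hazard 0.010 (halved in the last row) and pool 150 only. Bias is arm minus controls, in points.

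| Scenario | Lipid-day match (total days) | Criterion plus baseline match |
|---|---|---|
| No effect | -0.8 to +2.4 | -1.9 to +1.0 (log-SD 0.3-0.42); 0.0 to +3.9 (0.7); +0.6 to +6.7 (1.0) |
| Both arms 10% shorter | +2.7 to +5.0 | see below |
| Both arms 25% shorter | +8.3 to +10.9 | see below |
| Both arms 10% longer | -3.8 to -2.3 | see below |
| Hazard halved, duration unchanged | -0.2 to +0.8 | not tabulated |

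Across the changed-duration rows the baseline alternative gives -0.8 to +1.1 (log-SD 0.42), -0.3 to +2.8 (0.7) and +0.8 to +4.9 (1.0). Dropping lipid days without adding the criterion gives +4.0 to +15.4 under no effect. If only one arm is 25% shorter, its true -7.5 to -6.7 appears as -2.9 to -1.2, and the other arm's true zero appears as +4.0 to +5.7.

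**Chance error for scale.** At an assumed 37.5% risk, SE = sqrt(0.375 x 0.625 x (1/25 + 1/24)) = 0.138, or 13.8 points. With the minimum 12 v 24 it is sqrt(0.375 x 0.625 x (1/12 + 1/24)) = 0.171, or 17.1 points.

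**The case against.** The strongest defence is that the current rule works in the case most readers would assume. With total lipid days and duration unaffected, its bias is small. Root-mean-square error under no effect is 13.4 points for the lipid-day match and 13.8 for the baseline alternative, and with poor chart judgement the alternative is worse. Comparing infants with similar lipid exposure is also a legitimate aim. The documents nowhere say that a regimen shifts lipid duration by 10% or 25%; Table 1 is only a guide, and no weaning rule is given for the historic infants. At 10% shifts the two approaches overlap when chart judgement is poor. All of this stands, and it is why the baseline comparison should be added rather than substituted.

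Three stronger readings are tempting and are not supported.

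- A reader might take lipid days to mean study-lipid days, cut short by the bilirubin stop, which raises the no-effect bias to +1.1 to +8.7 points. The protocol uses a separate term for study lipid, and historic infants received none, so total days is the more natural reading. A definition settles it.
- A reader might infer that the comparison of time to enteral autonomy with controls is forced toward no difference. The two durations are related, but autonomy in controls is timed from the start of enteral feeding, Smoflipid can reach zero while PN continues, and no bias in that endpoint has been calculated.
- A reader might say that lipid days are not collected for controls. The control list names PN days and lipid dose but not lipid days. However, it also calls for the same information as for prospective patients, and the match cannot be done without lipid days.

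What the defence does not answer is that the rule is safe only if treatment leaves lipid duration alone. The protocol does not establish that, and its own rules allow otherwise.

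**Conclusion.** The point holds in a limited form. Selection of controls rests first on a quantity that treatment can change, while the baseline criterion that defines the prospective cohort is not asked of them. With total lipid days and unchanged duration the consequence is small, roughly -1 to +2 points. If a regimen changes duration, the lipid-day match can hide or reverse part of the effect; at an assumed 25% shortening in both arms the bias is about +8 to +11 points. These sizes rest wholly on assumed durations, hazards and chart-review accuracy, and the documents determine neither size nor direction.

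A reader might conclude that the primary comparison is invalid or that lipid-day matching should go. Neither follows: chance error in this pilot is larger than the likely shift, the randomised Smoflipid versus reduced-Intralipid comparison is untouched, and bare deletion performs worse than the current rule. This is a cheap improvement.

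**What to change.** 1. In Historic Controls, add to eligibility the anticipated PN need of four or more weeks. Judge it by a pre-specified rule from chart data available at surgery, before outcomes are abstracted.
2. Among controls meeting (1), add a comparison matched on baseline variables only: diagnosis stratum, birth gestational age and birth weight. Report it beside the lipid-day-matched comparison, and show both if they disagree. Do not drop the lipid-day match without (1).
3. Define lipid days as total days on parenteral lipid, counted the same way in all groups, and report them by group.

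The cost is a few sentences in Historic Controls and Statistical Considerations, one explicit data item, one extra analysis and a chart screen of 2016-2017 candidates. No prospective patients, visits or blood draws are added.

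There are two downsides. Retrospective judgement of PN need may be poor, which erodes the gain. Fewer than 24 controls may also qualify: in simulation this occurred in 12-27% of pools of 60 at an assumed median of 25 lipid days, in at most 1.4% at a median of 32, and never with a pool of 150. If it happens, use all who qualify and state the number.

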 - i. Each patient's chart will be reviewed for documentation of retinopathy of prematurity or bronchopulmonary dysplasia (chronic lung disease). The absence or presence of these diseases at the time of discharge will be noted for each study patient, particularly those patients born prematurely at less than 37 weeks gestation.
- d. Length of Stay:
 - i. An ICU length of stay will be calculated for each patient based on their admit date and discharge date from the Riley NICU.
 - ii. For patients transferred to another unit prior to discharge the transfer date will also be documented. For these patients a NICU length of stay and total hospital length of stay will be calculated.
- e. Laboratory monitoring (see Table 2 below for reference schedule):
 - i. Effort will be made to draw all study lab tests along with other standard of care, routinely scheduled labs.
 - ii. The schedule outlined here is a schedule of minimum laboratory work to be obtained. These studies may be obtained more often by the patient's primary clinical team. Any lab test obtained by the primary team within 3 days for weekly labs or within one week for less frequent labs will be used in place of the research lab test.
 - iii. Of note all lab tests listed could be considered standard of care, with the exception of INR.
 - iv. Essential fatty acid profiles will be obtained every 4 weeks (28 days) while receiving study lipid regimen.
 - 1. Blood volume needed 0.3-1mL
 - 2. Considered standard of care in any patient on alternative lipid dosing, such as patients enrolled in this study.
 - 3. If diagnosed with essential fatty acid disorder, defined as triene:tetraene ratio >0.05:
 - a. If Smoflipid dose is less than 3 g/kg/d, SMOF will be increased by 0.5 g/kg/d or to 3 g/kg/d maximum
 - b. Those receiving Smoflipid at 3 g/kg/d will be changed to Intralipid at current Smoflipid dose
 - c. Those receiving Intralipid will have their dose increased by 0.5 g/kg/d to maximum of 3 g/kg/d
 - v. Total and fractionated bilirubin levels will be monitored at least once weekly (7 days)
 - vi. Liver function panel and gamma-glutamyl transferase (GGT) will be monitored at least every 2 weeks (14 days).
 - vii. Triglyceride levels will be monitored within the first 48 hours of lipid initiation and then once weekly (7 days).

1. If triglyceride level >250 mg/dL will decrease dose of study lipid by 1g/kg/d to minimum of 2 g/kg/d of Smoflipid or 1 g/kg/d three days per week for Intralipid

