	Blood Volume (mL)	3.1	2.8	0.8	2.2	1.7	0.5	0.8	2.2	1.7	0.5	0.8	2.2	1.7

f. Neurologic Follow-up:

i. ASQ-3 at 2 years of age:

1. All prospective patients will have an ASQ-3 obtained during the 2nd year of life (age 2 year 0 day to 2 year 364 days).
2. ASQ-3 will be obtained in one of three manners:
 - a. In person: if patient has previously scheduled appointment at Riley
 - b. Via phone: if able to confirm identity of parent or guardian
 - c. Via mail (electronic or standard): if able to confirm proper mailing address of patient and parent/guardian
3. ASQ-3 will be completed by the subject's parent or guardian with the aid of one of the primary investigators.
4. If the subject receives a score within the "monitoring zone" or below threshold of "normal" in any developmental area:
 - a. Parent/guardian will be notified of this score
 - b. If known developmental delays exist will document if patient is receiving services for delay.
 - c. If no previously known developmental delay will refer patient to their primary care physician for further developmental screening and referral for proper services and follow-up.

g. Stopping study Lipid:

- i. Once a study subject reaches one of the following parameters they will stop receiving study lipid, whichever parameter occurs first:
 1. Maximum time of 12 weeks (84 days).
 2. Cholestasis with direct bilirubin of ≥ 3 mg/dL on two consecutive lab draws at least 5-7 days apart.
 3. Lipid or parenteral nutrition discontinuation for more than one week (7 days).
 4. Subject is discharged home or transferred from Riley Hospital for Children.

- ii. Once a subject reaches one of these time points, their lipid treatment, including lipid choice and dose, will be at the discretion of their primary treating physician.
- iii. Subjects will continue to be followed by the research team in order to have the following information documented:
 - 1. Anthropometric measurements at 36 weeks corrected gestational age.
 - 2. Follow-up anthropometric measurements at 2 – 3 weeks after stopping study lipid or at the time of discharge.
 - 3. Follow-up laboratory testing at 2 – 3 weeks after stopping study lipid if still admitted to Riley Hospital for Children.
 - 4. Documentation of prematurity complications.
 - 5. Discharge and/or transfer date to determine length of stay.
 - 6. ASQ-3 screen during the second year of life.

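### No fatty-acid profile is planned at enrolment, so deficiency that develops on study lipid cannot be told from deficiency already present

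*Combined protocol and SAP*

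**What the plan says.** Study Objectives, item 2.b, lists "Essential fatty acid profile differences and development of deficiency" as a secondary outcome and names no time points. The neighbouring laboratory objectives do name a starting value: item 2.e has "Transaminase, alkaline phosphatase, GGT levels at enrollment, every 4 week time point, and end of study" and item 2.f has "Triglyceride concentration at baseline, weekly, and end of study".

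Study Procedures, item 3.e.iv, sets the sampling: "Essential fatty acid profiles will be obtained every 4 weeks (28 days) while receiving study lipid regimen". Table 2 shows EFA at weeks 4, 8 and 12 and in the follow-up column at 2-3 weeks. Item 3.e.iv.3 defines deficiency as a triene:tetraene ratio above 0.05 and attaches a change of dose or product to it, for example "Those receiving Smoflipid at 3 g/kg/d will be changed to Intralipid at current Smoflipid dose".

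Infants may enter "regardless of postmenstrual or corrected gestational age", and the exclusion criteria do not mention EFA status. Once study lipid stops (item 3.g.ii), "their lipid treatment, including lipid choice and dose, will be at the discretion of their primary treating physician".

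Statistical Considerations tabulates the proportion with EFA deficiency, compares groups with Fisher's exact test, and uses mixed models for repeated continuous measures, between groups and within groups over time. It has no rule for deficiency at entry or for samples taken off study lipid.

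**The concern.** Development of deficiency is a question about incidence: who was not deficient at the start and became so on study lipid. With a first sample at week 4, a raised ratio may have arisen on study lipid or have been carried in. The within-group profile analysis has the same gap, since its earliest value follows four weeks of treatment.

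Later samples cannot stand in for the missing one. A ratio above 0.05 changes the regimen, so in infants who cross the threshold at week 4, the week 8 and week 12 values reflect the modified regimen.

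A smaller second issue concerns infants who stop study lipid before the first scheduled sample. The next required sample may come after a period on whatever lipid the physician chose, or on none.

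**Working it through.** **1. Is a week-0 sample really absent?** Table columns can shift in text extraction, so the check uses the stated blood volumes and assumes that they add across tests. TG is triglyceride, FB fractionated bilirubin, HFP hepatic function panel, PLT platelets.

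- Week 5 (TG + FB) = 0.5 mL; week 2 (TG + HFP + GGT) = 0.8 mL; INR = 1.7 mL (item 3.e.viii).
- Week 1 (TG + FB + PLT + INR) = 2.8 mL, so PLT = 2.8 − 0.5 − 1.7 = 0.6 mL.
- Week 4 (TG + HFP + GGT + PLT + EFA) = 1.7 mL, so EFA = 1.7 − 0.8 − 0.6 = 0.3 mL. This is the lower end of the range in item 3.e.iv.1: "Blood volume needed 0.3-1mL".
- Week 0 without EFA = 0.8 + 0.6 + 1.7 = 3.1 mL, exactly the stated figure. With EFA it would be 3.4 mL.
- The 13 volumes for weeks 0-12 sum to 21.0 mL. The follow-up draw with EFA is 0.8 + 0.3 + 0.6 + 1.7 = 3.4 mL, and 21.0 + 3.4 = 24.4 mL, the stated total.

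The plan's total is reproduced only if week 0 has no EFA.

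**2. What would the week-4 proportion measure?** Let p0 be the share deficient at entry, s the share of those still deficient at week 4, and i the incidence among the rest. The observed proportion is p0·s + (1 − p0)·i. The documents give none of these, so the values below are assumptions, with i = 10%.

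| p0 | s = 1 | s = 0.5 |
|---|---|---|
| 10% | 19% | 14% |
| 20% | 28% | 18% |
| 30% | 37% | 22% |

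The same 10% incidence can therefore appear as anything from 14% to 37%.

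**3. How much does one infant weigh?** 1/25 = 4.0 points and 1/12 = 8.3 points. If both arms share the same p0 of 10-30%, the binomial probability that they differ by three or more infants deficient at entry is 0.23 to 0.44 with 25 per arm, and 0.08 to 0.26 with 12 per arm.

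**4. Which infants may lack an on-lipid sample?** The first sample is due at day 28. Item 3.e.ii lets a clinical result within one week replace it, so one from about day 21 (28 − 7) can serve. For an infant who stops earlier:

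- If still admitted (stopped for cholestasis, for more than 7 days without lipid or parenteral nutrition, or under an individual stopping criterion), the only required sample is 2-3 weeks later, off study lipid.
- If discharge comes first, item 3.e.xi has the sample drawn within 3 days before leaving, possibly still on study lipid.
- If transferred, the position is unclear. Item 3.e.xi covers all enrolled infants, while item 3.g.iii.3 limits follow-up laboratory tests to those still admitted.

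**The case against.** The strongest reply is randomisation. Allocation is stratified and uses concealed envelopes, so deficiency at entry is balanced between the prospective arms in expectation, and Fisher's exact test already allows for chance imbalance. This stands. A reader might infer that the missing baseline biases the between-arm comparison, or that existing cases are charged to one arm; the documents do not support that. The probabilities in step 3 describe imprecision, not bias.

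Three further replies also stand in part:

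- Inclusion requires an anticipated four or more weeks of parenteral nutrition, so stopping before week 4 is not the expected course.
- The follow-up sample has its own column and its own post-study heading, and data are to be summarised at each time point. Nothing says that it decides who counts as deficient; the plan is silent.
- How much deficiency is carried in is unknown. The protocol itself answers deficiency with Intralipid or more of it, which makes earlier soy-based lipid a doubtful source.

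It can also be said that objective 2.b promises no change from baseline. Yet its wording concerns development, and the analysis plans comparison over time. Weeks 4, 8 and 12 give neither incidence nor change from entry.

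Finally, this is one secondary outcome in a feasibility pilot, and the documents do not call EFA deficiency the main safety concern of lipid reduction; the Background raises growth and neurodevelopment. That limits the weight of the point but does not remove it.

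**Conclusion.** The point holds in a limited form. No baseline EFA profile is planned, so incident deficiency under objective 2.b cannot be identified and change in the profile cannot be measured from entry. The schedule and the reproduced 24.4 mL total establish this without assumptions. Its numerical effect depends on rates of deficiency at entry that the documents do not give; steps 2 and 3 show a range under assumed values.

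Randomisation protects the comparison of on-study deficiency between the prospective arms in expectation. It does not protect the comparison with historic controls, whose laboratory values are recorded only where available.

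On early stopping, a reader might infer that every such infant has only an off-lipid sample. That goes too far, because pre-discharge and substituted clinical samples may be on study lipid. What remains is that infants who stop before about week 3 to 4 and stay admitted may have no on-lipid value; their number is not given. The primary endpoint is unaffected. The change is worth making because it is cheap and a missed baseline cannot be recovered.

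**What to change.** - **Baseline.** Add the EFA profile to the existing week-0 draw and specify its timing relative to the first study-lipid infusion, since item 3.e.vii allows the first triglyceride sample up to 48 hours after initiation.
- **Definition.** Count deficiency as developed when the ratio first exceeds 0.05 on study lipid in an infant not above it at week 0. Report the overall proportion alongside, and use week 0 as baseline in the profile model.
- **Sample status.** Classify each sample as on or off study lipid by its date, and keep off-lipid follow-up samples out of the development count. Report how many infants have no on-lipid sample. Requiring a profile at the last on-lipid draw would not work reliably: when stopping means more than 7 days without lipid or parenteral nutrition, that draw has passed before it is known to be the last.
- **Text to settle.** State how a week-0 result relates to the dose and product rule in item 3.e.iv.3. Reconcile item 3.e.xi with item 3.g.iii.3 on who has follow-up laboratory tests, including infants transferred out.

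Cost: one more assay and a small extra blood volume. The week-0 draw rises from 3.1 mL to 3.4 mL (+0.3) or 4.1 mL (+1), and the total from 24.4 mL to 24.7 or 25.4 mL. The protocol's standard-of-care remark refers to infants on alternative lipid dosing, so who pays for a pre-treatment assay should be checked. The definitions and sample labels need only text. A baseline in the prospective arms does not repair the historic comparison; report how many controls have any profile.
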